We will begin Specific Aim #3 after a 3-month lead in phase, during which we ensure that all performance targets from Specific Aim #2 are being reliably measured. This aim will include administration of a series of patient, caregiver, and provider surveys as well as analysis of the quality benchmarks mentioned above. Specifically, we propose to perform a prospective, matched cohort comparative effectiveness study of eligible patients receiving care within the multidisciplinary environment versus matched controls concurrently receiving usual, serial care in the same healthcare system.

Eligibility criteria:

Multidisciplinary cases will have an untreated but biopsy-confirmed lung cancer diagnosed, preferably within 8 weeks of screening for study eligibility. Therefore, patients will still need either a staging evaluation or selection of first line therapy, the types of decision-making most often required in lung cancer care.

Controls will be selected from the pool of patients receiving usual ('serial') care within the same institution. Two serial care controls will be matched to each multidisciplinary care case. To be eligible for inclusion, a serial care patient must have an untreated biopsy-confirmed lung cancer, diagnosed preferably within an 8 week window surrounding the diagnosis of the case to whom he/she will be matched (4 weeks prior through 4 weeks after the case's diagnosis), and will be matched hierarchically based on several matching criteria: clinical stage, performance status, insurance status, race, and age range.

All multidisciplinary clinic patients will be screened for eligibility before their initial clinic visit. If a patient is determined to be eligible to participate in Specific Aim #3, they will be approached for consent to the study by the clinical research professionals during their initial visit.

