- consensus management recommendations

Multidisciplinary clinic experience

- date of clinic visit
- details of patient experience in clinic
- treatment decisions made

Tumor characteristics (pre and post-op)

- details of T-category
 - 1) tumor size
 - 2) tumor laterality
 - 3) site of tumor invasion (if any)
- details of N-category
 - 1) number and details of suspected lymph nodes
 - 2) number and details of pathologically examined lymph nodes
- details of M-category: location and details of metastatic disease (if any)
- histology
- grade
- cumulative AJCC staging (clinical and pathologic)

Details of treatment

- surgery
- chemotherapy
- radiation therapy
- palliative/hospice care only
- timeline and outcomes of therapy

Benchmarks/Endpoints

- Patient survival** – as measured from the time from cancer diagnosis to death or data censor.
- Timeliness of care** – aggregate time from enrollment to specific care delivery endpoint; compared to British Thoracic Society recommendations.
- Thoroughness of staging** – proportion of patients with histologically confirmed (i.e., biopsied) stage-defining lesion

Appropriateness of treatment selection – Stage I or II: surgery (or radiation therapy with documented contraindication to surgery or patient refusal) Stage III: chemotherapy and radiation therapy with or without surgery Stage IV: systemic therapy (or palliative care with documented patient refusal or contraindication to systemic therapy)

Timeliness of communication – official, verifiable communication of management decisions with providers inside and outside the multidisciplinary program and official, verifiable communication of management plans with patients and their care-givers.

Survey response rate – for patients, for caregivers, for clinical providers; number of responses versus number administered

Survey responses –measured by qualitative analysis of completed surveys

Inclusion criteria

All patients who undergo care for lung cancer or an undiagnosed lung mass within the Baptist Memorial Health Care Corporation's hospitals from January 1, 2009 until the end of the defined study period will be eligible for inclusion in the data collection for this study. In addition, caregivers of patients within the same institution and within the study window, clinical care providers (doctors and nurses) who have taken care of patients within the eligible institutions during the study window.

Exclusion criteria

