Models for categorical outcomes: Assuming Y_i represents whether the patient receives stage-appropriate care (yes/no), and G_i represents whether patient is in multidisciplinary program or matched control, and X_i represents other confounders except matching variables. The conditional fixed effect model can be expressed as $\text{Log}(p(Y_i=1)/p(Y_i=0)) = \beta * G_i + \gamma X_i$. Note that intercept and matching variables are not estimated. The exponent of β is the odds ratio of receiving stage-appropriate care between multidisciplinary v. control. For other categorical outcomes, models and interpretations are similar.

Models for timeliness of care: The timeliness of care is measured in days: for example, days from the first diagnostic imaging test (earliest date of chest X-ray or CT scan) to receiving the actual treatment (surgery, chemotherapy, radiation, or hospice care); days from the first diagnostic imaging test to multidisciplinary clinic visit, and days from multidisciplinary clinic visit to treatment commencement. These variables are inherently right skewed and can be fit with Gamma distribution. In the fixed effects generalized linear model, $\text{Log}(\text{days}_i) = \beta * G_i + \gamma X_i$, the shape and scale parameters of the gamma distribution will be empirically determined based on all observations in each group. The exponent of β is the geometric mean difference of days (similar to median difference) between multidisciplinary program and controls.

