Models for survival events: All patients will be followed up for at least one year from the beginning of the study (with a median of 1.5 year). The follow up time will be longer if the starting time is retrospectively tracked back to the date of first imaging diagnosis. Assuming t_i represents the time (days) from the first imaging diagnosis to death, $h(t_i)$ is the corresponding hazard function, the proportional hazard model is $\text{log}(h(t_i)) = \beta * G_i + \gamma X_i$. The exponent of β is the hazard ratio of survival between multidisciplinary program and controls. In addition, the proportional hazard assumption in the model will be examined visually by plotting - $\text{log}(\text{log}(\text{survival}))$ and time, and also by statistically testing by adding time interaction in the model. We will also visually compare the survival curve difference using Kaplan-Meier estimate and log rank test for curve difference between two groups. Finally, the Fine-Gray competing risk model will be used to compare lung cancer specific death.

Analyses for self-reported satisfaction with care and quality of life: patient, caregiver, and provider satisfaction scores are measured using survey methods. Surveys also are used to measure quality of life, including health related quality of life and depression/anxiety (in patients and caregivers) and caregiver burden (in caregivers only). For each measure, summary scores will be calculated according to the instructions in each survey instrument. Although the scores based on Likert scales can be treated as continuous variables, we will dichotomize the satisfaction scores as satisfactory (scores 5-6 on a 6-point scale) and unsatisfactory (scores 1-4), to correspond to our benchmark criteria. Descriptive analysis and logistic model similar to the previous analyses will be used.

Potential benefits to subjects/others.

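### Overall survival has conflicting time origins that precede consent and no delayed entry, so the curves are inflated and the hazard ratio is biased if the origin-to-consent gap differs between arms

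*Protocol*

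**What the plan says.** The SAP (Statistical Methods, Supplemental) names overall survival as the primary endpoint.

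- **Origin in the endpoint list.** Protocol, Benchmarks/Endpoints, defines survival "as measured from the time from cancer diagnosis to death or data censor".
- **Origin in the model.** Protocol, Models for survival events, defines the Cox time as one that "represents the time (days) from the first imaging diagnosis to death". The same paragraph opens by counting follow-up from the start of the study, then adds: "The follow up time will be longer if the starting time is retrospectively tracked back to the date of first imaging diagnosis". The start is thus left conditional. No separate origin is given for the Kaplan-Meier, log-rank or Fine-Gray analyses.
- **SAP.** The available text specifies a stratified Cox model with no origin and no entry time. Part of the SAP was not available for review.
- **Consent, multidisciplinary arm.** Protocol, Eligibility criteria: "they will be approached for consent to the study by the clinical research professionals during their initial visit". Diagnosis should be "preferably within 8 weeks of screening for study eligibility".
- **Consent, serial arm.** The same section has controls approached only once a matching case has consented. They are to be "diagnosed preferably within an 8 week window surrounding the diagnosis of the case to whom he/she will be matched".
- **Later change.** The SAP replaced individual 1:2 matching with frequency matching. Its matching variables do not include entry time.

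**The concern.** Both arms need a biopsy-confirmed cancer before enrolment, so first imaging and diagnosis both come before consent. Nobody who enrols can have died in that interval. If the clock starts at either date without delayed entry, the interval is counted as time at risk although no death could be observed in it. There are three consequences:

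1. Survival curves are too high in both arms, even with equal gaps.
2. If the gap distribution differs between arms, the arm with the longer gap looks better when care makes no difference. Stratifying on the matching variables does not remove this.
3. The two origins give the same patient different survival times, so the primary result depends on which passage the analyst follows.

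The plan does not treat the gap as fixed. For cases it lists "days from the first diagnostic imaging test to multidisciplinary clinic visit" as a timeliness outcome.

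**Working it through.** **Inputs from the Protocol (Sample size calculation).** Stage mix 30% I/II, 30% III, 40% IV. One-year mortality 15%, 30%, 50%; two-year mortality 30%, 50%, 70%. Sample 150 and 300, with 40% mortality. Follow-up is at least 1 year with a median of 1.5 (Models for survival events), possibly up to 5 years after the last enrolment (Length of study). **Not given anywhere:** the origin-to-consent gap in either arm. All gaps below are assumptions.

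**Check against the plan's mortality.** The plan has no figure for the gap, but its 40% mortality can be approached. With a constant hazard through the two-year rates, mortality at 1.5 years is 1 − (0.3 × 0.7^0.75 + 0.3 × 0.5^0.75 + 0.4 × 0.3^0.75) = 1 − 0.570 = 43%. This is close to 40% and inside the stated 30–50% range.

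**Curve inflation, equal gaps.** True one-year survival is 0.3 × 0.85 + 0.3 × 0.70 + 0.4 × 0.50 = 66.5%. With g weeks of event-free time counted first, the curve at one year shows S(1 − g/52.18), where S(t) = 0.3 × 0.85^t + 0.3 × 0.70^t + 0.4 × 0.50^t.

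| Assumed gap | Apparent one-year survival | Patients who would die before they could consent |
|---|---|---|
| 4 weeks | 68.5% | 3.3% |
| 8 weeks | 70.6% | 6.4% |
| 12 weeks | 72.7% | 9.4% |

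**Hazard ratio, imaging origin.** Below, HR is multidisciplinary versus serial, so a value above 1 means multidisciplinary care looks worse. The true HR is 1. Hazards are −ln(1 − two-year mortality)/2 = 0.178, 0.347 and 0.602 per year. Gaps are gamma distributed (shape 2), patients are alive at consent, and the Cox model is stratified by stage. HRs come from 300,000 versus 600,000 simulated patients, and type I error from 6,000 trials of 150 versus 300.

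| Mean gap, weeks (multidisciplinary, serial) | HR, 1–2 y | Type I error | HR, 5–6.5 y | Type I error |
|---|---|---|---|---|
| 8, 8 | 1.00 | 5.2% | 1.00 | 4.8% |
| 10, 8 | 0.97 | 5.1% | 0.99 | 4.8% |
| 12, 8 | 0.93 | 7.5% | 0.97 | 5.9% |
| 8, 10 | 1.04 | not run | 1.02 | not run |
| 8, 12 | 1.08 | 8.1% | 1.04 | 6.8% |

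A second simulation used one-year mortality for the hazards and a 6-week base gap. It gave 0.96 or 1.04 for a 2-week difference and 0.93 or 1.08 for 4 weeks.

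**Closed-form check.** Deaths expected: 450 × 0.40 = 180. SE of log HR = 1/√(180 × 1/3 × 2/3) = 0.158. For HR 1.08, ln 1.08/0.158 = 0.487, so two-sided rejection is P(Z > 1.473) + P(Z < −2.447) = 7.0% + 0.7% = 7.8%. Relative to the target effect, ln 1.08/ln 1.25 = 0.077/0.223, about one third.

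**Diagnosis origin, windows honoured.** Case gap uniform over 0–8 weeks; control diagnosed within 4 weeks either side of the case; control consent at the later of case consent or own diagnosis, plus a lag. Mean lags of 0, 1, 2 and 4 weeks give HR 1.00, 1.02, 1.03 and 1.08 at 1–2 years' follow-up.

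**If care does differ.** A target of 1.25 (serial versus multidisciplinary) is 1/1.25 = 0.80 in the orientation used here. A serial gap 4 weeks longer moves it to 0.86 (1/1.164). A multidisciplinary gap 4 weeks longer moves it to 0.74 (1/1.349).

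**Delayed entry.** With entry at consent, the first simulation returned 0.995–1.006 and the second 0.993–1.003 when the true HR was 1. In these scenarios gap length is unrelated to prognosis.

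**The case against.** The strongest reply has five parts.

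- **The start may be neither date.** The survival paragraph opens with follow-up from the start of the study and makes back-dating conditional, so a reader could take study start as the default. That reading is possible, but the same paragraph then defines the model time from first imaging and the endpoint list says diagnosis. The ambiguity stands.
- **SAP silence is weak evidence.** The text is a short supplement and part of the SAP was unavailable. That is fair: the claim covers only the available text.
- **The design limits the gap.** Both arms must be untreated, and controls are pre-screened from weekly lists before a case consents. This stands as a limit on any difference from diagnosis. It does not fix consent dates or the imaging-to-diagnosis interval, and both diagnosis windows are stated as preferences. The Statistical analysis section lists an entry criterion among the matching factors without defining it.
- **Every effect size is assumed.** True. No gap is documented, and differences of 2 weeks or less matter little.
- **A consent clock as primary is debatable.** Control consent depends on research logistics, so this clock can align the arms at different points in the disease. That stands, and it favours keeping diagnosis with delayed entry.

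A reader might infer that the plan favours multidisciplinary care. The documents do not support that. The stated sequence tends to make the serial gap longer, which pushes the HR above 1. At HR 1.075 (0.072/0.158 = 0.457 SE), the chance of a false multidisciplinary benefit falls from 2.5% to about 0.8%, and that of false harm rises to about 6.6%. On that path the risk is a hidden benefit.

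**Conclusion.** The contradiction in origin is certain on the available text and should be fixed. Curve inflation follows whenever either pre-consent origin is used without delayed entry. It is about 2, 4 or 6 percentage points at one year for assumed gaps of 4, 8 or 12 weeks.

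Bias in the hazard ratio is conditional. It is absent if the gap has the same distribution in both arms, minor at a 2-week difference, and about one third of the target log hazard ratio at 4 weeks with 1 to 2 years' follow-up. It roughly halves with 5 or more years. The direction is not certain: the consent sequence suggests a longer serial gap, but the SAP does not say whether that sequence survived the change to frequency matching. It would go too far to conclude that the trial's hazard ratio is biased, since no document reports a gap or shows that the arms differ.

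The sizes rest on constant hazards within stage and assumed gap distributions. The stage IV rates do not fit a constant hazard exactly (0.69 per year from year one, 0.60 averaged over two years), but hazards from either set of rates gave nearly the same results.

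**What to change.** 1. State one origin in Benchmarks/Endpoints, in Models for survival events and in the SAP. Keep cancer diagnosis, the formal endpoint definition.
2. Count patients as at risk only from the consent date (delayed entry) in the Cox model and in the Kaplan-Meier and log-rank comparisons. In SAS, PROC PHREG accepts an entry time.
3. Add a consent-origin analysis as a sensitivity. It also serves Fine-Gray, which would need extra weighting under delayed entry.
4. Report the diagnosis-to-consent and imaging-to-consent intervals by arm.
5. Do not present back-dating to imaging as added follow-up.

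**Cost.** Mainly wording and one extra variable. The enrolment date is already needed, because timeliness is defined as "aggregate time from enrollment to specific care delivery endpoint". Early risk sets become slightly smaller. The SAP is written in the past tense, so some re-analysis is needed if results exist, and it should be labelled as such. Residual bias remains if gap length is related to prognosis: in assumed scenarios with true HR 1 and within-stage frailty, delayed entry left 0.97–1.04 and a consent origin 0.99–1.03.

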As noted above, extensive data will be compiled that encompasses the full scope of patients' experience of care for lung cancer, from initial discovery to the conclusion of treatment. To evaluate the effectiveness of patient care, extensive analysis will be performed by researchers at the University of Memphis, School of Public Health, (co-investigators on the grant, signed to a Baptist-approved subcontract) with specific attention given to timeliness of care, completeness of staging, surgical resection rate, and stage-appropriate treatment rate. The de-identified, aggregate results of this analysis will be shared with process engineers at the University of Wisconsin-Madison (co-investigators, signed to a Baptist-approved subcontract) who will use computer simulation modeling to map, measure and optimize the efficiency of patient flow through the healthcare system. Finally, the effectiveness of the clinic will be evaluated using survival time as an outcome, using data from institutional records, supplemented by the Social Security Death Index.

ADOPTION – The adoption domain of the RE-AIM framework will focus on the characteristics of physicians who participate (by referring patients into the clinic or directly providing care within the multidisciplinary environment) versus those who do not participate. This information will be collected by comparing multidisciplinary thoracic program referral records to the list of relevant specialty physicians credentialed within the BMHCC catchment area of the multidisciplinary program. Physician characteristics to be compared include demographics (age, gender) and training/practice (specialty area, years of practice, practice setting).

IMPLEMENTATION/MAINTENANCE – will be measured for the multidisciplinary program as a function of Specific Aim #2.

Data or samples to be collected

All patients will be provided a unique database identifier to anonymize research data.

Patient demographics

sex

race

date of birth

- zip code of residence
- health insurance coverage
- clinical assessment
 - performance status
 - family history of cancer
- comorbidities
- smoking history
- additional risk factors

Pre-treatment care experience

- method of detection
- disease related procedures
 - radiographic scans
 - biopsy procedures
 - provider office visits
 - evaluation for chosen treatment modality

Multidisciplinary conference experience

- date of presentation
- details of patient history at time of presentation

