Patients who do not have a biopsy-confirmed lung cancer are excluded from this study.

Vulnerable populations

No vulnerable populations will be included in this study.

Length of study

Generally, this project is funded by a 3-year grant, which starts on February 3, 2014 and ends on February 2, 2017, with the possibility of extension by up to 1 year (February 2, 2018). However, because of the need to demonstrate program sustainability, we will continue to measure the quality benchmarks that constitute specific aim 2, as a key ongoing quality improvement exercise for the clinical multidisciplinary program. In addition, because of the primary endpoint, overall survival, it may be necessary to continue long-term follow up of patients for up to 5 years after enrollment of the final patient in specific aim 3, the comparative effectiveness study.

Number of study sites

Specific Aim #3 involves the Baptist Memorial Health Care Corporation system.

Number of subjects

Specific Aim #3 will match 150 patients undergoing care in the multidisciplinary clinic with up to 300 similar patients concurrently undergoing serial care for a total of 450 patients.

However, for the process engineering sub-aim, and to examine the domains of Reach and Adoption, all patients who receive lung cancer care from January 1, 2009, onward, and the clinical providers of lung cancer care, will need to be accessible for limited data abstraction.

Sample size calculation

150 multidisciplinary clinic patients matched 1:2 with 300 serial care patients = 450 patients for Specific Aim #3. The 150 multidisciplinary clinic patients will all be selected from the estimated 960 patients examined in Specific Aim #2. We powered the prospective comparative cohort study in Specific Aim #3 based on the survival analysis. Assuming power = 80%, alpha= 0.05, two sided test, mortality rate 40%, and hazard ratio 1.25, we estimate the total sample size 427 using Cox regression procedure in PASS 11. Since Baptist Health Care System manages >800 new cases each year, 300 of which are expected to be seen in multidisciplinary clinic, in practice, we conservatively expect to be able to recruit 150 cases from multidisciplinary clinic and 300 matched serial care controls (1:2 match) in 18 months.

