### **Statistical Methods (Supplemental)**

The study was designed with overall survival as the primary endpoint. The design provided 80% power, with alpha of 0.05, to detect a hazard ratio of 1.25 between patients receiving multidisciplinary care and serial care. We targeted enrollment of 150 patients on the multidisciplinary arm and 300 patients on the serial care arm, matched by clinical stage (based on the initial diagnostic CT scan), performance status, insurance status, race, and age range. After initiation of the study, it was determined that the individual 1:2 matching strategy was not attaining high level matches within the allotted parallel time frame for the required number of subjects. To accommodate this change the following revisions were made to the statistical methodology. A frequency matching strategy was used based on the matching variables (age, sex, and histology were controlled for as a model covariate for better numerical efficiency). Crude comparisons between groups were made using standard univariate two sample methods. Comparative analyses were then conducted using matching variables as strata, per original design, with the strata now allowing multiple cases and controls per match group (frequency matching). Specifically, analyses were designed based on conditional logistic regression for each binary endpoint and stratified cox proportional hazards models for survival endpoints. Models were further adjusted to include age, sex, and histology in addition to the adjustment for strata described above. For each outcome, additional statistical models were evaluated controlling for matching variables as covariates in unconditional analyses. All analyses were conducted in SAS Version 9.4 (Cary, NC) with a type-I error rate of 0.05.

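### Lung-cancer-specific death is compared only by Fine-Gray, whose ratio also reflects arm differences in other-cause death; cause-specific models for both causes should accompany it

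*Protocol*

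**What the plan says.** The protocol's Statistical analysis section (Models for survival events) sets out a proportional hazards model in which the outcome "represents the time (days) from the first imaging diagnosis to death", with Kaplan-Meier curves and a log-rank test. It then closes with one sentence on cause of death: "Finally, the Fine-Gray competing risk model will be used to compare lung cancer specific death". No cause-specific hazard model, other-cause death model or cumulative incidence curve by cause is named.

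Overall survival is primary in both documents. The protocol's Length of study section refers to longer follow-up "because of the primary endpoint, overall survival", and the SAP says "The study was designed with overall survival as the primary endpoint". The Benchmarks/Endpoints list defines survival without regard to cause, "as measured from the time from cancer diagnosis to death or data censor". Lung-cancer-specific death is in neither that list nor the endpoint list under Study design, so it is supplementary.

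The SAP (Statistical Methods, Supplemental) assigns "stratified cox proportional hazards models for survival endpoints". The text available mentions neither Fine-Gray nor lung-cancer-specific death. On the source of deaths, the protocol's Methods section (Effectiveness) says "using data from institutional records, supplemented by the Social Security Death Index". Neither document gives a rule for assigning cause, or says whether a treatment-related death counts as a lung-cancer death.

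**The concern.** Fine-Gray keeps patients who have died of another cause in the risk set for lung-cancer death. Its ratio describes how the arms differ in the cumulative incidence of lung-cancer death. That is a legitimate quantity, but it combines two effects: the effect on the rate of lung-cancer death among the living, and the effect on how many patients die of something else first.

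The arms could well differ in other-cause death. Multidisciplinary care is evaluated on resection rate and stage-appropriate treatment, so the mix of surgery, chemotherapy and radiation is expected to differ. The arms are also not randomised. Comorbidities and smoking are collected, but they are not matching variables and are not among the SAP's named covariates (age, sex, histology).

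If other-cause death differs, the Fine-Gray ratio departs from 1 with no difference in lung-cancer mortality rates. More other-cause death in the clinic arm pushes it below 1, and less pushes it above 1. With no other-cause model beside it, a reader cannot tell this shift from an effect on lung-cancer death.

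**Working it through.** The documents give no figure for lung-cancer-specific death, so there is none to reproduce. The check asks how far Fine-Gray moves when the lung-cancer hazard is the same in both arms.

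**Inputs from the protocol (Sample size calculation; Models for survival events).** Stage mix is 30% I/II, 30% III and 40% IV. One-year mortality is 15%, 30%, 50%; two-year mortality is 30%, 50%, 70%. Allocation is 150:300, median follow-up 1.5 years.

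- One year: 0.30×0.15 + 0.30×0.30 + 0.40×0.50 = 0.335
- Two years: 0.30×0.30 + 0.30×0.50 + 0.40×0.70 = 0.520
- Midpoint, used here for 1.5 years: 0.4275, inside the protocol's 30-50% range and near the 40% in its sample size calculation
- Constant total hazard in serial care: λ = −ln(1 − 0.4275)/1.5 = 0.3718 per year

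**Assumptions not in the documents.** Other causes make up a share s = 10%, 20% or 30% of the serial-care death hazard. The clinic arm multiplies the other-cause hazard by m = 2 or 0.5. Hazards are constant.

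**Formulas.**

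- λ1 = (1 − s)λ in both arms; λ2 = sλ in serial care and m·sλ in the clinic arm
- Cumulative incidence of lung-cancer death: F1(t) = λ1/(λ1 + λ2) × [1 − exp(−(λ1 + λ2)t)]
- Example, s = 0.20, m = 2, t = 1.5: clinic 0.2974/0.4461 × (1 − exp(−0.6692)) = 0.325; serial 0.80 × 0.4275 = 0.342
- Fine-Gray ratio θ: the large-sample solution of the partial-likelihood score equation with complete follow-up. Each arm's risk set is proportional to 1 − F1(t), weighted 1/3 and 2/3.
- All-cause hazard ratio: (1 − s) + s·m
- SE of ln θ with 450 patients: 1/√(D × 1/3 × 2/3), where D is the expected number of lung-cancer deaths

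**Results (true cause-specific ratio for lung-cancer death = 1).**

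| m | s | θ, 1.5 y | D, 1.5 y | SE | shift/SE | θ, 5 y | all-cause HR |
|---|---|---|---|---|---|---|---|
| 2 | 10% | 0.97 | 172 | 0.16 | 0.18 | 0.91 | 1.10 |
| 2 | 20% | 0.94 | 151 | 0.17 | 0.33 | 0.84 | 1.20 |
| 2 | 30% | 0.92 | 131 | 0.19 | 0.45 | 0.79 | 1.30 |
| 0.5 | 10% | 1.02 | 174 | 0.16 | 0.09 | 1.05 | 0.95 |
| 0.5 | 20% | 1.03 | 155 | 0.17 | 0.17 | 1.10 | 0.90 |
| 0.5 | 30% | 1.04 | 136 | 0.18 | 0.24 | 1.15 | 0.85 |

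**Five years.** The single-time-point shortcut ln(1 − F1,clinic)/ln(1 − F1,serial) gives 0.87-0.75 for doubling and 1.08-1.19 for halving. That is a ratio of cumulative subdistribution hazards. Proportionality fails here, so a Fine-Gray fit does not return it; the table shows the fitted limits. With 335, 292 and 251 lung-cancer deaths under doubling, the five-year shifts are about 0.9, 1.4 and 1.8 standard errors.

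**Simulation check.** With 1.5 million patients per scenario, 40% serial-care mortality at 1.5 years and censoring uniform over 1-2 years, doubling gave Fine-Gray ratios of 0.98, 0.94 and 0.92 and all-cause ratios of 1.10, 1.19 and 1.30. Cause-specific Cox models for lung-cancer death returned 1.00, 0.99 and 1.00.

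**The case against.** Fine-Gray is a recognised way to compare the cumulative incidence of one cause of death, and this is one closing sentence on an outcome in neither endpoint list. The primary analysis is all-cause. In every doubling scenario it moves toward harm while Fine-Gray moves toward apparent benefit, so excess deaths could not disappear from the main result. The other-cause shares and multipliers are assumed, and at planned follow-up the shift is small beside sampling error. Five years is only a contingency in the protocol, and the five-year figures carry a constant hazard out to 84% serial-care mortality (1 − exp(−0.3718×5)), which the documents do not state. The SAP may also have dropped Fine-Gray.

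All of this stands, and it limits the point to interpretation of a supplementary result. It does not supply the missing analysis. A report showing all-cause harm beside a lung-cancer-specific ratio below 1 would have nothing in the plan to explain it. The shift is a feature of what is being estimated, so a larger sample would not remove it. The SAP's silence on Fine-Gray is itself something to settle.

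A reader might go further and infer that treatment-related deaths would be reported as lung-cancer benefit, so that a safety problem reads as efficacy. The documents do not support that. It requires such deaths to be coded as other-cause, and no coding rule is given; if they are coded as lung-cancer deaths, the distortion does not arise this way. The primary analysis counts them in either case.

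**Conclusion.** The point holds as a minor one. The protocol's only stated comparison of lung-cancer-specific death cannot separate an effect on lung-cancer mortality from a difference in other-cause mortality, and the SAP text leaves its status open. With equal lung-cancer hazards and an assumed 10-30% other-cause share, the Fine-Gray ratio at 1.5 years is about 0.97-0.92 if the clinic arm doubles the other-cause hazard and 1.02-1.04 if it halves it, under half a standard error throughout.

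The shift matters more if follow-up is extended. With complete five-year follow-up the ranges are 0.91-0.79 and 1.05-1.15, and the lower extreme is about the size of the design effect (1/1.25 = 0.80). These figures rest on constant hazards and on shares and multipliers that the documents do not give. Neither the primary conclusion on overall survival nor the use of Fine-Gray to describe absolute risk is in question.

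**What to change.** Compare the arms with cause-specific Cox models for lung-cancer death and, separately, for other-cause death, using the same strata and covariates as the overall survival model. Keep Fine-Gray or cumulative incidence curves for both causes as the description of absolute risk. In the SAP, state which of these analyses are retained and how cause of death is assigned, including treatment-related death. Say that any lung-cancer-specific difference will be read only alongside the other-cause and all-cause results.

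The cost is two more model fits and a few SAP sentences. The models use the cause-of-death data that Fine-Gray already needs, but the assignment rule has to be written for any of them to be interpretable. Event counts are modest, especially for other-cause death: in the scenarios above, about 16-74 such deaths among 450 patients by 1.5 years. That model will be imprecise, and a null result from it should not be read as showing no difference.
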